10.2 Baseline Values

Unless otherwise noted, baseline is defined as the last non-missing value recorded before the first dose of study drug. Unscheduled visits will be used in the determination of baseline values, when applicable.

10.3 Adjustments for Covariates

The model for the primary, secondary, and exploratory efficacy analyses will include adjustments for the following covariates:

Continuous secondary and exploratory efficacy endpoints (excluding Functional Outcomes and Quality of Life Endpoint) analyzed using ANCOVA models will include baseline vIGA-ADTM score and age group as a categorical covariate and the baseline value as a continuous covariate (see Section 11.2 and Section 11.3).

10.4 Handling of Dropouts or Missing Data

Imputation of Missing Efficacy Data

The principal method for handling of missing data will be multiple imputation (MI). MI will be performed separately using estimand requirements (MI estimand) and without estimand requirements (MI non-estimand). MI estimand will be considered primary.

For the MI estimand analyses investigator assessments including vIGA-ADTM, EASI, %BSA based on data not collected at in-person visits (e.g., due to COVID-19 considerations) will be set to missing. Multiple imputation will be done as described in more detail below. Afterwards, using the MI estimand dataset, subjects who prematurely discontinue treatment due to an AE or lack of efficacy and subjects who use a specified prohibited medication prior to Week 8 will be considered a treatment failure at the time of treatment discontinuation or the date of initiation of prohibited medications for the primary and dichotomized secondary endpoints. For the continuous secondary endpoint of change from baseline BSA, BSA value will be set to the baseline value for the treatment failures specified above. For the MI non-estimand analyses, all visit assessments (including in-clinic and not in-clinic) will be included. Treatment failures will not be implemented as described previously for the MI estimand analyses.

For both the MI estimand and MI non-estimand analyses, 100 imputations will be generated using PROC MI of SAS. Fully Conditional Specification (FCS) model using the regression method will be used with the response (e.g., vIGA-ADTM score) at prior post-baseline visits, baseline vIGA-ADTM score, baseline age group, baseline value of the corresponding endpoint (for endpoints other than vIGA-ADTM score), and treatment group as covariates. The ROUND, MINIMUM and MAXIMUM options will be utilized to ensure imputed values are within appropriate ranges and precision. The seed to be used in all MI models is 20230421.

Two sets of MI datasets (MI estimand and MI non-estimand) will be generated for the vIGA-ADTM scores, EASI scores, %BSA, and PP-NRS results separately. Response status (Yes, No) will be derived from the imputed scores in each MI dataset. Analysis of each primary and secondary outcome will then be performed for each of the relevant MI datasets. The results of the 100 analyses will be transformed into a normal statistic and combined into a single analysis using PROC MIANALYZE.

The imputation models may be modified based on the actual data if there is an issue in model convergence.

Sensitivity analyses of the primary and secondary endpoints will be performed using MI (non-estimand), last observation carried forward (LOCF), observed cases (OC) (i.e., no imputation), and imputing missing data as Treatment Failures (TF). Only missing data up to Week 8 will be imputed. Missing data at the Week 9 Follow-up visit will be summarized as OC only.

LOCF: The last observed value will be carried forward for any subsequent missing values. Baseline values will not be carried forward. Unscheduled visits will be included.

TF: missing data will be imputed as treatment failures for responder endpoint.

Missing functional outcomes, quality of life endpoints or safety endpoints will not be imputed.

Average weekly PP-NRS scores will be calculated for all nominal visits as the average of 7 daily post-baseline PP-NRS scores prior to and including the values assessed on the visit date. If daily PP-NRS scores are missing for more than 3 days in a 7-day period, the average weekly PP-NRS score will be set to missing. If two or more scores are reported on the same day, the maximum score on that day will be used.

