5. DETERMINATION OF SAMPLE SIZE

It is estimated that the proportion of subjects who will achieve a vIGA-ADTM score of 0 or 1 and at least a 2-grade reduction from Baseline to Week 8 will be 45% for subjects receiving tapinarof compared with 25% for subjects receiving vehicle control, based upon the Phase 2 results. With 400 subjects randomized in a 2:1 ratio (267 subjects receiving tapinarof, and 133 subjects receiving vehicle control), this will provide 97.2% power for statistical significance (2-sided p <0.05). The power is calculated from a Fisher Exact sample size calculation. It is assumed that 15% of the subjects receiving tapinarof will be lost to follow-up by 8 weeks compared with 30% of the subjects receiving vehicle control. These subjects will be included in the primary analysis using the multiple imputation method.

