11. METHODS OF EFFICACY ANALYSIS

11.1 Primary Efficacy Analyses

The primary estimand of interest is the composite estimand in a patient population offered treatment with tapinar fcream, 1% as compared to vehicle. Interest is focused on the treatment

effect measured by the ratio of response rates at Week 8. The primary efficacy endpoint for treatment effectiveness is proportion of subjects who achieve vIGA-ADTM score of clear (0) or almost clear (1) and at least a 2-grade reduction from Baseline at Week 8. Subjects who prematurely discontinue treatment due to an AE or lack of efficacy and subjects who use a prohibited medication with significant impact on efficacy evaluations prior to Week 8 will be considered treatment failure as of the start of the intercurrent event. Discontinuing treatment due to adverse event or lack of efficacy will be based on data recorded on the End of Treatment eCRF. Analysis will be based only on data collected at in-person visits for investigator assessments.

Estimand Attribute	Description
Treatment	tapinar of cream, 1% compared to vehicle
Population	Intent-to-treat
Variable of interest	Proportion of subjects who achieve vIGA-AD TM score of clear (0) or almost clear (1) and at least a 2-grade reduction from Baseline at Week 8
Intercurrent event handling	Subjects who prematurely discontinue treatment due to an AE or lack of efficacy and subjects who use a prohibited medication with significant impact on efficacy evaluations prior to Week 8 will be considered treatment failure. Investigator assessments will only include data collected at inperson visits.
Summary measure	Ratio of response rates at Week 8

The primary efficacy comparison will test the following hypotheses:

- H₀: The proportion of subjects who achieve a vIGA-ADTM score of clear (0) or almost clear (1) and at least a 2-grade reduction from Baseline at Week 8 is equal between tapinar of cream, 1% and vehicle cream;
- H₁: The proportion of subjects who achieve a vIGA-ADTM score of clear (0) or almost clear (1) and at least a 2-grade reduction from Baseline at Week 8 is different between the tapinar of cream, 1% and vehicle cream.

The primary efficacy endpoint will be analyzed using a Cochran–Mantel–Haenszel (CMH) test stratified by vIGA-ADTM score at Baseline (vIGA-ADTM scores of 3 or 4) and age group (2-6 yrs, 7-11 yrs, 12-17 yrs, 18+ yrs) based on the ITT population using the MI estimand approach.

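### The primary imputation keeps in-person scores recorded after prohibited medication, which can raise the imputed response of other dropouts; the effect is modest and generally works against tapinarof

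*SAP*

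**What the plan says.** SAP 10.4 sets the order of the primary (MI estimand) analysis in three steps.

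1. Investigator assessments "based on data not collected at in-person visits (e.g., due to COVID-19 considerations) will be set to missing".
2. Imputation: "100 imputations will be generated using PROC MI of SAS". The "Fully Conditional Specification (FCS) model using the regression method will be used with the response (e.g., vIGA-ADTM score) at prior post-baseline visits", together with baseline vIGA-AD, age group and treatment group.
3. The failure rule: "Afterwards, using the MI estimand dataset, subjects who prematurely discontinue treatment due to an AE or lack of efficacy" are made failures, and "subjects who use a specified prohibited medication prior to Week 8 will be considered a treatment failure". For %BSA, failures are returned to their baseline value.

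SAP 11.1 describes the medications in question as those that significantly affect the efficacy evaluations, and says that these subjects "will be considered treatment failure as of the start of the intercurrent event". Nothing in the visible text removes in-person scores recorded after such a medication before step 2.

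Protocol 4.6.1 makes withdrawal for prohibited medication optional. A user may continue study drug if the investigator and Medical Monitor agree that the medication does not interfere, so later clinic scores can exist. Protocol 10.6 names multiple imputation but does not set the order of steps.

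**The concern.** The failure rule repairs the users' own outcomes, because they end as failures whatever their scores. It does not touch the values already drawn for other dropouts. Those draws come from a regression fitted partly to scores that another treatment may have improved. A subject who was doing badly at Week 4 and then left is imputed in part from people who were also doing badly, took a prohibited product, and looked better at Week 8. Under a composite estimand, such a score says nothing useful about what the dropout would have achieved on assigned treatment.

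What is at stake is the primary ratio of response rates. The same order applies to the secondary endpoints analysed by the MI estimand approach. The plan already accepts the logic of the remedy: it blanks remote-visit scores before imputing because they do not fit the estimand.

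**Working it through.** **The plan's own figure.** SAP 5 assumes that response "will be 45% for subjects receiving tapinarof compared with 25% for subjects receiving vehicle control", with 267 and 133 subjects, two-sided 0.05, Fisher exact, and states 97.2% power. Exact enumeration gives 97.6%, and a pooled z calculation gives 98.0%. The figure is reproduced to within a point. The documents give no figure for the effect of imputation order.

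**Inputs.**
- From SAP 5: 45% and 25% response; loss of 15% on tapinarof (0.15 × 267 ≈ 40) and 30% on vehicle (0.30 × 133 ≈ 40).
- Assumed, because the documents are silent: rate of prohibited-medication use by arm, its benefit in vIGA-AD grades, and the share of users with later scores (all, unless stated).

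**Main simulation.** vIGA-AD at Weeks 1, 2, 4 and 8 was calibrated to 45%/25%, with loss depending on the Week 2 score. Imputation was by sequential regression on earlier visits, baseline vIGA-AD, age group and treatment, rounded to 0–4, with 20 imputations and 250 trials per scenario. Two orders were compared: as written, and with post-medication scores set to missing first. Failure was assigned last in both.

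Since users are failures either way, whole-arm shift ≈ loss fraction × shift in dropouts' imputed response. For example, on vehicle at 5%/10% use and 2 grades: 0.30 × 8.3 = 2.5 points. Shifts below are as written minus corrected, in percentage points; the simulation standard error of the dropout shifts is at most 0.3.

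| Use, tapinarof/vehicle | Benefit (grades) | Dropouts, vehicle | Dropouts, tapinarof | Whole arm, vehicle | Whole arm, tapinarof |
|---|---|---|---|---|---|
| 2%/5% | 1 | +1.6 | +0.9 | +0.5 | +0.1 |
| 2%/5% | 2 | +3.8 | +1.7 | +1.1 | +0.3 |
| 5%/10% | 1 | +3.8 | +2.4 | +1.1 | +0.4 |
| 5%/10% | 2 | +8.3 | +4.5 | +2.5 | +0.7 |
| 5%/5% | 1 | +1.7 | +2.1 | +0.5 | +0.3 |
| 5%/5% | 2 | +4.2 | +4.5 | +1.2 | +0.7 |
| 10%/10% | 1 | +3.5 | +4.1 | +1.0 | +0.6 |
| 10%/10% | 2 | +8.4 | +7.8 | +2.5 | +1.2 |
| 5%/10% | 0 | −0.5 | −0.3 | −0.1 | about 0 |
| 5%/10%, half of users with later scores | 2 | +3.9 | +2.6 | +1.2 | +0.4 |

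**Against the truth** (composite outcome on full data), vehicle arm at 5%/10% use:
- 1 grade: 26.3% as written, 25.2% corrected, 24.7% true.
- 2 grades: 27.1% as written, 24.6% corrected, 23.8% true.

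**Effect on the planning ratio.** Vehicle = 0.25 + 0.30 × shift; tapinarof = 0.45 + 0.15 × shift.
- No shift: 0.45 / 0.25 = 1.80; Fisher power 97.6%.
- 2%/5%, 1 grade: (0.45 + 0.15 × 0.0088) / (0.25 + 0.30 × 0.016) = 0.4513 / 0.2548 = 1.77; power 97.2%.
- 5%/10%, 2 grades: (0.45 + 0.15 × 0.0450) / (0.25 + 0.30 × 0.0829) = 0.4568 / 0.2749 = 1.66; power 94.2%.

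These powers treat imputed values as observed, so only the differences between them mean anything.

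**Two further models, both at assumed 4%/10% use.**
- With 60% of users reaching success: vehicle 25.2% as written, 24.1% corrected, 23.6% true; ratio 1.76, 1.83 and 1.87.
- With a 2-grade benefit: ratio 1.74, 1.96 and 2.01. If the tapinarof rate is taken as 45% under both orders, the vehicle rates are 0.45 / 1.74 = 25.9% and 0.45 / 1.96 = 23.0%, about 3 points apart. That sets the upper end of the range. With lack-of-efficacy discontinuers added and their early-termination scores windowed to Week 8, the ratios are 1.96, 2.12 and 2.10.

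**The case against.** The strongest opposing case has five parts.

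- **The size rests on assumptions.** Use by arm and benefit appear nowhere in the documents, and with no benefit there is no inflation. This stands: the direction can be argued from the text, but the size cannot.
- **The affected group should be small.** Protocol 4.6.1 lets a user continue when the medication is judged not to interfere, while the failure rule concerns medication that does. This stands as a limit, and halving the users with later scores roughly halves the shift. The group need not be empty: withdrawal is optional, and the SAP 11.2 rule for weekly PP-NRS provides for scores on or after the event.
- **A force pulls the other way.** SAP 7 assigns early-termination scores to analysis visits by study day, with the Week 8 window opening at Day 43, so poor scores from lack-of-efficacy discontinuers also train the model. In one check (4%/10% use, 60% of users succeeding, 4%/10% lack-of-efficacy discontinuation within the 15%/30% loss), the plan as written gave vehicle 24.2% against a true 24.0%, and a ratio of 1.96 against 1.98. The net error can therefore be close to zero. That is two effects cancelling under particular rates, not a property of the method. In the model above that included these discontinuers, removing only post-medication scores still brought the ratio closer to the truth.
- **Other analyses avoid the model.** Treatment-failure, LOCF, observed-case and tipping-point analyses do not use it. True, but MI non-estimand has the same exposure, and none of them corrects the primary estimate.
- **Some specification is unseen.** The SAP revision history mentions example SAS code in 10.4 that is not in the supplied text. It might prepare the input differently, but the prose gives no sign of that.

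**Conclusion.** The point holds as a modest flaw in the order of steps. As written, in-person scores after a specified prohibited medication inform the imputation of other dropouts and, if the medication helps, bias their imputed response upward. Under assumed use of 2–5% on tapinarof and 5–10% on vehicle and a 1 to 2 grade benefit, the whole-arm vehicle rate rises by roughly 0.5 to 3 points. The effect is about nil without benefit, and smaller if users are withdrawn or if poor early-termination scores also train the model.

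Two stronger readings are tempting, and the documents support neither.
- A reader might infer that the inflation falls mainly on vehicle dropouts because vehicle subjects use more prohibited medication. No use rates are given, and with equal use the dropouts' shift is about the same in both arms. The vehicle arm as a whole still moves about twice as far, because assumed loss is 30% against 15%.
- A reader might infer that the order flatters the product. In every scenario above with a benefit, the vehicle arm moves more, so the ratio is understated and some power is lost. Use much heavier on tapinarof could change that; it was not simulated.

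**What to change.** Amend SAP 10.4 for the MI estimand dataset only. Before PROC MI, set to missing every vIGA-AD, EASI, %BSA and PP-NRS value recorded after the start of a specified prohibited medication; then impute; then assign failure. For weekly PP-NRS, the 7-day rule already in SAP 11.2 can define which averages are affected. Leave MI non-estimand unchanged, and report the number of scores removed per arm.

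Keep early-termination scores recorded at discontinuation for an AE or lack of efficacy. Blanking everything after any intercurrent event would discard them, and nothing here shows that they distort the imputation.

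The cost is one sentence and one data step, agreed before database lock and unblinding. It needs no new data and no change to Protocol 10.6, which leaves the order open. The change does not remove the error entirely: in the main simulation the corrected vehicle rate stayed 0.5 to 0.8 points above the truth (25.2% vs 24.7%; 24.6% vs 23.8%). Label: free improvement, of modest size.

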m. If needed, laboratory testing at the Follow-up visit for ongoing AEs or abnormal laboratory values.

n. Urine sample collection for urinalysis is not required at the Baseline Visit if it has been \leq 14 days since samples were collected at Screening and the results of those analyses were not clinically significant.

o. Blood sample for PK will be collected in a subset of subjects. Sample to be collected prior to study drug application in clinic. Informed consent/assent will be required.

p. Photography will be performed in a subgroup of subjects at selected study sites. Informed consent/assent and photographic release will be required.

q. The vIGA-ADTM assessment should be performed before the %BSA and EASI assessments. The subject's scalp should be excluded from the vIGA-ADTM, %BSA, and EASI calculations.

r. The LTS assessment consists of an Investigator-assessed and a subject (or caregiver)-assessed component. Both the Investigator-assessed LTS and subject (or caregiver)-assessed LTS should be completed within 2 hours post-dose at Weeks 1, 2 and 4. At Week 8 and the ET visit, when study drug is not applied, the LTS should be completed when other assessments are completed. If the subject (or caregiver) is applying study drug to "sensitive areas" (face, neck, skin folds, axilla, inframammary, anal crux, and/or genitalia), the Investigator will also complete a separate LTS assessment for each sensitive area where study drug is being applied.

s. Subjects (or Caregivers) should perform the PP-NRS assessment daily and record the results in their diary. When subjects dose in the clinic on study visit days, subjects will not complete the diary at home; application time and PP-NRS will be recorded in the clinic.

t. Subjects will be instructed on when and how to complete diaries.

u. Subjects will be instructed to apply study drug QD at the approximate same time each day, based on subject preference.

v. At clinic visits, study drug will be applied after safety and efficacy assessments have been conducted (except for LTS at Weeks 1, 2 and 4).

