7.9 Early Termination Visit

Subjects who withdraw early from the study will be asked to return to the study site to complete Early Termination assessments as follows:

- Urine pregnancy test (females of child-bearing potential)
- Brief physical examination
- Vital signs measurement
- Blood sample collection for clinical laboratory tests
- Urinalysis
- ECG recording (at a subset of study sites only)
- vIGA-AD™ score (excluding subject's scalp)
- %BSA affected calculation (excluding subject's scalp)
- EASI (excluding subject's scalp)
- [REDACTED]
- [REDACTED]
- PP-NRS
- [REDACTED]
- [REDACTED]
- Investigator-assessed LTS
- Subject-assessed LTS
- AE recording
- Concomitant medication recording
- Collect subject diaries

- Review subject diaries for treatment compliance
- Collect study drug

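### Itch scores from returned Week 5 to 7 diaries are not used to impute a missing Week 8 PP-NRS score; the effect is small and conditional, and the remedy costs almost nothing

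*SAP*

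**What the plan says.** Protocol Table 1, footnote s: "Subjects (or Caregivers) should perform the PP-NRS assessment daily and record the results in their diary". The diary dispensed at Week 4 is collected at Week 8 or at the ET visit, where Protocol 7.9 lists "Collect subject diaries" and a PP-NRS assessment.

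SAP 10.4: "Average weekly PP-NRS scores will be calculated for all nominal visits as the average of 7 daily post-baseline PP-NRS scores". A week with more than 3 of its 7 days missing gets no mean. On treatment, the clinic visits are Weeks 1, 2, 4 and 8; Weeks 3 and 6 are phone contacts.

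For imputation, SAP 10.4 specifies a regression model that "will be used with the response (e.g., vIGA-ADTM score) at prior post-baseline visits", plus baseline vIGA-AD score, age group, the baseline value of the endpoint and treatment. The text names no diary week between visits, and it allows changes to the model only for convergence problems.

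SAP 7 assigns ET and unscheduled visits to an analysis visit by study day: Days 22-42 to Week 4, and Day 43 onward to Week 8. Within a window, the visit closest to the target day is used.

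Under SAP 10.4 and 11.2, subjects who stop treatment for an adverse event or lack of efficacy, or who use specified prohibited medication, count as failures whatever is imputed.

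**The concern.** vIGA-AD and EASI are scored at visits, so the last visit is usually all there is to impute from. PP-NRS is different: the trial collects it every day. Under the SAP text, a subject can hand in several weeks of itch scores after Week 4 and still have Week 8 imputed as if nothing were known after Week 4.

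The endpoint is the proportion of subjects aged 12 or over, with baseline PP-NRS of at least 4, who improve by at least 4 points. It is formally tested, in a subset of the trial. If subjects leave because itch has recently worsened, a model that stops at Week 4 does not see the worsening and imputes too many responders. Even when leaving is unrelated to itch, discarding the best predictors of Week 8 costs some precision. The itch sensitivity analyses (imputation without the failure rule, LOCF, observed cases, missing as failure) do not bring in the diary weeks, and the tipping-point analysis covers only the primary endpoint.

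**Working it through.** **1. The plan's own figure.** SAP 5 states power only for the primary endpoint: 97.2% for "45% for subjects receiving tapinarof compared with 25% for subjects receiving vehicle control" with "267 subjects receiving tapinarof, and 133 subjects receiving vehicle control". Enumerating the two-sided Fisher test exactly gives 97.6%; the pooled normal approximation gives 98.0%. The stated figure is reproduced to within a point, and this issue does not change it. No power is stated for itch.

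**2. Size of the itch subset.** Each age group has a minimum of about 15%. Ages 12 and over are therefore at least 15 + 15 = 30% and at most 100 - 15 - 15 = 70% of 400, or 120 to 280 subjects before the baseline criterion. At 2:1 that is about 80/40 to 187/93. Applying the SAP 5 dropout of 15% and 30% gives:
- 0.15 × 80 = 12 and 0.30 × 40 = 12 without Week 8;
- at the top of the range, 0.15 × 187 = 28 and 0.30 × 93 = 28.

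**3. Who is affected.** Visit weeks end on Day 7k + 1, so Week 5 is Days 30-36, Week 6 is Days 37-43 and Week 7 is Days 44-50.
- *ET visit on Days 32-42 after an attended Week 4 visit.* The ET visit falls in the Week 4 window, at least 32 - 29 = 3 days from target. A Week 4 visit within its ±2-day allowance is closer and wins. Diary days in Week 5 and part of Week 6 go unused.
- *Week 8 attendee with more than 3 of the last 7 days missing.* Week 8 is imputed, although the diary handed in that day may hold complete Weeks 5-7.
- *ET visit from Day 43.* SAP 7 maps it to Week 8 but treats ET visits separately from nominal visits, and SAP 10.4 gives weekly means to nominal visits. Read literally, there is no Week 8 mean and it is imputed; read the other way, it is observed.

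**4. What later weeks add.** Assume a subject-level SD of 1.5 scaled by f(t) = √(t/8), a residual SD of 1.3 and weekly AR(1) correlation ρ. Given baseline, cov(j,k) = 1.5² f(j) f(k) + 1.3² ρ^|j-k|, and Week 8 variance is 2.25 + 1.69 = 3.94. R² for Week 8:

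| Predictor weeks | ρ = 0.5 | ρ = 0.7 | ρ = 0.9 |
|---|---|---|---|
| 1, 2, 4 (SAP) | 0.288 | 0.365 | 0.662 |
| 1-4 | 0.294 | 0.366 | 0.662 |
| 1-5 | 0.368 | 0.465 | 0.746 |
| 1-6 | 0.463 | 0.588 | 0.828 |
| 1-7 | 0.625 | 0.754 | 0.912 |

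Week 3 adds under 0.01. The gain comes from Weeks 5-7.

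**5. Bias and precision, every dropout imputed.** The simulation used the covariance above, baseline mean 6.8 (SD 1.5, limited to 4-10), true response of about 42% and 18%, and dropout of about 15% and 30%. Log-odds of leaving per itch point were 0, 0.25 or 0.5. Bias under the SAP model, in percentage points:

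| ρ | Log-odds | Tapinarof | Vehicle | Difference |
|---|---|---|---|---|
| 0.5 | 0.25 | +0.48 | +0.63 | -0.15 |
| 0.5 | 0.5 | +0.99 | +1.05 | -0.06 |
| 0.7 | 0.25 | +0.42 | +0.58 | -0.16 |
| 0.7 | 0.5 | +0.82 | +0.96 | -0.14 |
| 0.9 | 0.25 | +0.26 | +0.31 | -0.05 |
| 0.9 | 0.5 | +0.44 | +0.39 | +0.05 |

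With all weeks as predictors and diaries returned, per-arm bias in these rows is at most 0.09 points. With log-odds 0, the SAP model's per-arm figures are within 0.12 points and its difference within 0.16, so shifts of this size in the difference are simulation noise. With diaries not returned, the difference is shifted about as under the SAP model.

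The standard error ratio (SAP model over all weeks) is 1.014 to 1.018; for example, 0.0912/0.0896 = 1.018 at 80/40 and 0.0597/0.0587 = 1.017 at 187/93. About 6% of tapinarof and 11-12% of vehicle subjects leave after Week 5, 6 or 7, where later diaries can help: at 80/40, roughly 0.062 × 80 = 5 and 0.116 × 40 = 5 subjects.

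**6. Only the cases that remain after the ET mapping.** A separate run with itch-dependent dropout, also on assumed parameters, gave per-arm overstatement of about 0.4 to 0.9 points, under 0.4 points in the difference, and a standard error about 2-3% larger.

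**The case against.** A reader might infer that the plan ignores the most recent itch of dropouts in general and so inflates the treatment effect. A scenario can be built to suggest this: 133/67 subjects, all leavers going in Weeks 5-7, all returning diaries, all imputed. It gives overstatement of 1.2-1.9 points (tapinarof) and 1.5-2.4 points (vehicle), with a standard error 5-7% smaller once all weeks are used. The documents do not support that reading, for these reasons:

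- **ET mapping.** On the natural reading of SAP 7, an ET visit from Day 43 supplies Week 8. In a similar set-up with ET visits after Weeks 6 and 7 mapped this way, the overstatement became an understatement of 0.9-1.0 (tapinarof) and 0.4-0.6 (vehicle).
- **Failure rule.** Someone who leaves because itch returned would often be recorded as lack of efficacy and count as a failure.
- **Diary return.** SAP 5 describes the dropouts as lost to follow-up. Such subjects may never hand in the diary dispensed at Week 4.
- **Direction.** Even the heavy scenario moves the difference against tapinarof: 1.86 - 2.40 = -0.54 points at ρ = 0.8, and 1.18 - 1.47 = -0.29 at ρ = 0.9. Itch is last in the fixed sequence, so no other test depends on it.

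These points stand, and they reduce the size. They do not remove the gap for the Days 32-42 group or for Week 8 attendees with sparse diaries, and the second case does not depend on dropouts returning anything. The Day 43 mapping helps only if the weekly mean applies to re-mapped visits, which SAP 10.4 does not say.

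One reservation: the SAP revision history mentions example SAS code in 10.4 that is not in the text available here. If that code lists further PP-NRS variables, part of the point falls away.

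**Conclusion.** The point holds in limited form. By its text, SAP 10.4 leaves returned Week 5-7 itch scores out of the PP-NRS imputation in two identifiable groups, and in a third if nominal visits is taken literally.

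Bias is conditional: it arises only if leaving depends on itch after Week 4 beyond what Weeks 1, 2 and 4 and the covariates explain. In that case each arm's response may be overstated by up to about 1 point. The difference moves by a few tenths of a point; the one positive value (+0.05) is within simulation noise. The standard error is about 1-3% larger, equivalent to about 2-6% of sample size (1.01² = 1.02, 1.03² = 1.06). No false-positive risk has been shown.

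All these sizes rest on means, SDs, correlations and dropout mechanisms that the documents do not give. The simulation in step 5 counts every dropout as imputed, so it is an upper bound on the share affected. The frequency of sparse Week 8 diaries is unknown. This is a point to consider: small, but nearly free to improve.

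**What to change.** In SAP 10.4, before database lock:

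1. Derive weekly PP-NRS means for each study week 1-8 from the dates in returned diaries, keeping the existing rule that at least 4 of 7 days must be present.
2. Add at least Weeks 5, 6 and 7 as predictors in the PP-NRS imputation model. Week 3 is optional. The existing convergence clause can serve as the fallback.
3. State that an ET visit mapped to Week 8 uses the 7-day mean ending on that visit, under the same 4-of-7 rule.

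If the primary model is to stay as it is, run the extended model as a sensitivity analysis and still make the third change, which removes an ambiguity in a formally tested endpoint.

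The cost is a few lines of SAP text and code. No new data are needed. Where diaries are not returned, the change gains essentially nothing.
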